#### Six-month follow-up

The six-month assessment will occur six-months after session 8 is completed (or was scheduled to be completed if a participant drops out of the intervention). This assessment will include 2 visits to the study site.

The measures collected will be identical to the post-treatment assessment. At visit 1, the participant will receive an actigraph to wear at home for 1 week, a sleep and medication diary to complete, and selected questionnaires will be administered. At visit 2, the participant will return the actigraph, diary, six-month fall log, and will complete additional questionnaires and provide a urine sample. The CURES database will also be queried to obtain data about prescriptions for controlled medications. Participants who complete the 6-month follow-up will receive \$50 for their travel and time.

# Amendment for telehealth option

Post-treatment follow-up assessment (begins at end of session 8)

Prior to intervention session 8 VVC visit, participants will receive by mail/pick-up the following items:

- Wrist actigraph
- Sleep diary
- Questionnaire packet
- Medication log
- Fall log
- Postage-paid return, insured Return Box to return the study materials (e.g.,actigraph)

Participants will also be instructed to go to the VA clinical laboratory to provide a urine sample.

At the end of session 8, the participant will be instructed to put on the actigraph to wear at home for 1 week and to complete the sleep and medication diary each day of that week.

One week later, a VVC post-treatment assessment visit will occur. At that visit, the participant will be administered selected questionnaires included in the baseline assessment. Participants will also be instructed to record any falls they experience over the next six months in the fall log. Participants will mail/deliver the actigraph and sleep diary back to the study office.

# Six-month follow-up assessment

A few days prior to the VVC visit, participants will receive by mail/pick-up the following items:

- Wrist actigraph
- Sleep diarv
- Questionnaire packet
- Medication log
- Postage-paid return, insured Return Box to return the study materials (e.g., actigraph, sleep diary and fall log)

Participants will also be instructed to go to the VA clinical laboratory to provide a urine sample.

Participants will wear the actigraph for 7 days and nights, complete the sleep diary, and answer the questionnaires over the course of two VVC visits.

#### Amendment for telephone option

If video connection is not possible due to technical issues (e.g., bandwidth connectivity issues, software problems, hardware issues), research staff will conduct the follow-up visits via telephone.

# Amendment for abbreviated mailed follow-up questionnaire

When a participant is unable to be contacted (e.g., due to a non-working phone number) or refuses to complete a follow-up assessment by video or telephone, the participant will be mailed an abbreviated assessment that includes three questionnaires from the approved follow-up assessment (i.e., ISI, Dbase-16, and sleeping pill use).

Amendment to add giftcards as an alternative patient compensation

The giftcards will serve as alternative subject payment if the subject did not receive original VA issued check compensation after a completed study visit. This addition to the protocol was added to reduce delayed payment compensation and maintain study integrity.

Follow-up for Missed Appointments

Participants who miss a study appointment will be telephoned by research staff on the day of the missed appointment. If the participant does not return the call within 10 days of the missed appointment, a letter will be sent that encourages the participant to contact the research office (see Missed Appointment Letter). If a participant has not returned an actigraph or Watch-PAT device, the letter will also include a paragraph about the importance of returning the device. If the participant does not return the device after 10 days from the date of the first letter, a second letter will be sent that explains that failure to return the device requires staff to submit a missing equipment report to VA police (see Failure to Return Device Letter).

# Potential Risks and Safety Plan

Benzodiazepine withdrawal symptoms: Symptoms are not common with withdrawal of low doses of benzodiazepines, but could include dizziness, anxiety, depression, and insomnia. The proposed intervention has a similar risk level to behavioral/ pharmacological strategies recommended by healthcare providers to adults as part of routine clinical care. Based on our pilot data and our team's collective clinical experience with low-dose hypnotic discontinuation, withdrawal symptoms that warrant protocol changes are uncommon. To reduce the risk of severe withdrawal symptoms, adults at high risk of complicated withdrawal or on high benzodiazepine doses (based on comorbidities, current prescriptions, and answers to assessment questions) will not be randomized to receive the intervention. Participants will be monitored weekly with the Clinical Institute Withdrawal Assessment-Benzodiazepine [CIWA-B] instrument and with weekly vital signs. If the participant is found to have mild symptoms of withdrawal based on select items from the CIWA-B or on mild changes in vital signs, a study physician (e.g., Drs. [name] or [name]) and the participant may decide to plateau the taper until the participant is ready to continue with the dose taper. If participants are found to have moderate, severe, or very severe scores on select items in the CIWA-B, er moderate or severe vital sign changes, or have worsening severed insomnia, the study physicians will discuss the patient's symptoms with a staff psychiatrist to determine whether the changes to the taper schedule are needed (including increasing or plateauing the dose) and whether the patient needs additional clinical evaluation. If the patient needs clinical evaluation, the participant will be escorted to the outpatient clinic or for life-threatening emergencies at our facility, we will call 911.

# Amendment for telehealth option

If a participant needs clinical evaluation during a VVC appointment, staff will advise the participant to seek medical care locally at the nearest emergency department, or for life-threatening emergencies, we will call 911.

- Confusion about duplicate hypnotic prescriptions: Participants may not understand that the hypnotic provided by the study (in blister packs or medication bottle) replaces the hypnotic that they were previously taking. This could result in participants taking both prescriptions at the same time, which would result in a higher dose than prescribed, and possible side-effects (e.g., daytime sleepiness, dizziness). To avoid confusion about duplicate hypnotic prescriptions, participants in both groups will be asked to bring all their medications to the first intervention session. The interventionist will identify the hypnotic that will be tapered and will place the bottle in a sealed envelope. A label will be affixed to the outside of the envelope that states, "Do not take this medication during the 8-week SWITCH study unless instructed by the study staff." The interventionist will explain that the participant will receive the same hypnotic either in a new medication bottle or in the blister packs and should put the old prescription in the sealed envelope in a safe location.
- Increased daytime sleepiness: Adjustments to the participant's sleep habits may result in some initial
  daytime sleepiness. Daytime sleepiness will be monitored during each weekly in-person intervention
  assessment with the Epworth Sleepiness Scale, and participants with increased daytime sleepiness will be
  counseled on the possibility of impaired cognition and increased fall and motor vehicle crash risk. If
  excessive daytime sleepiness is thought to be due to study-related sleep restriction (as opposed to, for
  example, a newly-prescribed medication from the individual's physician), the prescribed sleep schedule will
  be adjusted.
- Mental discomfort: The minor risks associated with completion of the questionnaires include tediousness, fatigue, and/or mental discomfort answering the items. Participants could also find wearing the actigraph

and home sleep apnea testing device (e.g., WatchPAT device) to be annoying or uncomfortable. To reduce the risk of mental discomfort among participants, research staff will be trained to recognize discomfort in participants, and they will be trained to remind participants of the voluntary nature of the research and the option for participants to decline participation in any portion of the research project.

- Falling during one-leg balance test: Participants could lose balance and fall during the one-leg balance test. To reduce the risk of falling during the one-leg balance test, research staff will place a gait belt around participants. For participants who use mobility aids, two research staff will perform the testing and additional steps such as placing a walker around the participant may also be employed.
- Skin irritation: The sensors worn for one night as part of the home sleep apnea testing device (e.g., WatchPAT device) and the actigraph wrist band worn for 7 days may cause skin irritation or an allergy. We have extensive experience using wrist actigraphy and the home sleep apnea testing devices such as the WatchPat system, and have chosen these devices because they are well-tolerated by participants. They are also substantially less burdensome than other objective methods of recording sleep (i.e., requiring the participant to spend a night in a sleep laboratory). Research staff will carefully review with participants potential skin problems associated with wearing the wrist actigraph and the home sleep apnea testing device sensors. Participants will be told to remove the device if they have any significant discomfort or any evidence of skin injury. Participants will have access to a research staff person, in case they have questions or concerns about the equipment. In addition, the company which makes the WatchPAT device has a 24-hour advice line that also provides troubleshooting support. Our monitoring devices are checked regularly to insure safe and proper operation. [name] (PI) will be notified immediately of any significant discomfort experienced by study participants.
- Confidentiality and privacy breach: There is risk of breach of privacy via unintentional disclosure of Protected Health Information, which could lead to embarrassment and fraud, which in turn could have negative financial impact on participants. To ensure confidentiality of the research data collected, all participants will have a unique identification number assigned that is not based on any identifying information. This identification number will be used for all computer databases, which will be stored behind a firewall on the VAGLA Health Services Research & Development (HSR&D)-managed server, as well as for hard copy data collection forms. Access to these databases and hard copy forms will be limited to the study's approved research staff and will not be transmitted. Research hypnotic tracking logs (that use subject identification numbers) will be maintained to ensure that all hypnotics that are prepared, dispensed. and disposed (if unused) are accounted for at all times. These hypnotic tracking logs will be shared with the VA research pharmacy (via a shared folder located behind a firewall). Consent forms and hard copies of data forms will be stored in locked file cabinets in locked offices with access limited to approved research staff, in the VAGLA Geriatric Research, Education and Clinical Center (GRECC) research offices. Electronic lists of names and contact information will be kept separate from other data in limited access folders on the VAGLA HSR&D-managed secure server behind a VA firewall. Data will be destroyed according to the Records Control Schedule.

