# Amendment for telehealth option

Intervention sessions conducted by VVC

Participants who receive the intervention sessions by VVC will receive the auto-generated and study-generated emails described above for the baseline assessments. The content of the intervention and taper schedules used to taper hypnotic use will be identical to the in-person sessions.

Prior to the first intervention session, the following materials will be mailed to participants:

- Notebook containing education materials for each session
- Sleep diaries for each week
- Blood pressure machine (if participant does not have a blood pressure machine at their home)
- Questionnaires (i.e., CIWA, ISI, ESS questionnaires) completed at sessions
- Postage-paid, self-addressed return envelopes to return questionnaires
- Medication for SGT group: 30-day supply plus Paper Taper Schedule in a sealed envelope to be opened at Session 1
- Medication for MTcap group: 3-week supply plus 3 weeks PRN plateau
- Postage-paid, pre-addressed, delivery box to return unused medication.

Additional medication will be mailed to participants over the course of the intervention according to the taper schedule for that group.

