# Amendment for telehealth option

Urine sample: Participants who receive the intervention by VVC/telephone will be asked to go to the VA clinical lab to provide a urine sample prior to the first intervention session.

Vital signs: The interventionist will assess respiratory rate and observe the participant measure their blood pressure and pulse via VVC at each session.

Daily sleep and habits diary: Participants will use the diary to record bedtime, wake time, total sleep time, time to fall asleep, time awake at night, number of awakenings, napping, exercise, alcohol use. Participants in the MTcap group only will also record their perceived hypnotic dose taken and their daytime function and sleep quality.

- MTcap (Masked Taper plus cognitive behavioral therapy-augmented program):
  - a. Hypnotic taper protocol: Participants will receive encapsulated hypnotics in a blister taper pack prepared by a non-VA compounding pharmacy. Participants will be informed that gradual dose reduction will occur during the program, but they will be blinded to the actual dose they receive each day. The planned rate of reduction of hypnotic will be about 25% per week. The final taper pack will consist of 4 placebo capsules (nights 1-4) and 3 empty blisters (nights 5-7). This planned rate of taper would yield a taper length similar to those reported in other studies, where the average length of taper was 49 days (range 6.5 to 84 days).
  - b. Cognitive behavioral therapy for insomnia-augmented program: The 8 sessions will incorporate the key components of CBTI (sleep restriction, stimulus control, cognitive restructuring, targeted sleep hygiene) and CBT targeting hypnotic withdrawal. Using the masked doses as a CBT tool, we will add exercises and concepts designed to address and alter expectations for hypnotics. A daily sleep/perceived hypnotic dose diary will be used as a tool for challenging expectancies about hypnotics, refining treatment recommendations, and adjusting the weekly plan.

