## Protocols for distribution of hypnotics

For both groups, a member of the research team will pick-up the medication bottle or blister packs from the VA Research Pharmacy and give it to the participant at the first intervention session. If the participant does not come to the appointment, the medication will be returned to the Research Pharmacy. If the Research Pharmacy is closed (e.g., the pharmacist has left for the day, is at a meeting), the medication will be stored either in a locked safe (located in Building 115, Room 328) or the locked narcotics box in the Clinical Research Center (CRC) in Building 500 on the West Los Angeles campus until the Pharmacy reopens or it can be given to the participant.

For participants seen on the Sepulveda campus, a research team member will transport the medication via personal car to Sepulveda. The medication will be placed in a locked bag and stored in the trunk during transport. The medication will be stored in a locked safe in Building 25/Room A137 until the participant receives it at the first session. If the participant does not come to the appointment, the medication will be returned to the safe.

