### Amendment for telehealth option

Medications will be mailed to participants following the same procedures used by the VA pharmacy service. Participants will also have the option of picking up the medication from our research staff at the Sepulveda VA or West Los Angeles Medical Center.

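### The session 1 step that seals and labels the old hypnotic bottle has no telehealth version, although study hypnotic may be mailed before that session

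*Combined protocol and SAP*

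**What the plan says.** Under Potential Risks and Safety Plan, the item on confusion about duplicate hypnotic prescriptions states that a participant may not realise the study supply replaces the existing one, may take both, and may become sleepy or dizzy. Participants in both arms are to bring all their medications to the first session. There, "The interventionist will identify the hypnotic that will be tapered and will place the bottle in a sealed envelope". A warning label goes on the outside, and the interventionist explains the replacement.

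For in-person participants, Protocols for distribution of hypnotics has a team member collect the study drug and "give it to the participant at the first intervention session". If the participant does not attend, the drug goes back to the Research Pharmacy or the safe.

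For telehealth, the amendment under Interventions says: "Prior to the first intervention session, the following materials will be mailed to participants". The list then gives one medication line per arm:

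- SGT+CBTI: "Medication for SGT group: 30-day supply plus Paper Taper Schedule in a sealed envelope to be opened at Session 1"
- MTcap: "Medication for MTcap group: 3-week supply plus 3 weeks PRN plateau"

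The amendment to the distribution section adds: "Medications will be mailed to participants following the same procedures used by the VA pharmacy service". It also gives participants the "option of picking up the medication from our research staff".

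**The concern.** The sealing step works in person because three things happen together: the old bottle is present, the interventionist can handle it, and the study drug has not yet been released. Telehealth breaks all three. The old bottle stays at home, the interventionist cannot touch it, and the study drug may already have arrived.

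The sponsor judged the confusion likely enough to warrant a physical reminder on top of the explanation. Followed as written, the plan gives remote participants the explanation without the reminder, and can put two supplies of the same hypnotic in the home before the explanation is given. These are older adults, and the Specific Aims themselves link hypnotic use to falls. What is at stake is participant safety; sample size, power and the analysis are not affected.

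**Working it through.** The plan gives no figure to reproduce. The check compares the in-person control with the telehealth and telephone text, and then sizes the exposure.

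**Step 1. Compare the control, part by part.**

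| Part of the control | In person | Telehealth or telephone |
|---|---|---|
| Old bottle available to the interventionist | Brought to session 1 | Not addressed |
| Old bottle sealed | By the interventionist | Nobody named |
| Warning label | Fixed to the envelope | No envelope or label on the mailing list |
| Explanation that study drug replaces it | Session 1 | Session 1, by video or telephone |
| Release of study drug | Session 1 | May be mailed before session 1, interval not stated |
| Study drug if session 1 is missed | Back to pharmacy or safe | Not addressed |

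On the last row, the mailing list includes a box for returning unused medication, but nothing says when it is to be used. The missed-appointment letters concern the actigraph and the sleep apnea device.

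**Step 2. Look for a remote version elsewhere.** The telehealth paragraph within the safety plan covers only the route to clinical evaluation. The video standard practices cover identity, privacy, location and an emergency contact. The telephone amendment for intervention sessions refers back to the video procedure. The pick-up option describes no sealing step. Other hands-on procedures were adapted: a paper ruler is mailed for neck circumference, and the interventionist will "observe the participant measure their blood pressure and pulse via VVC at each session". The omission therefore looks like an oversight.

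**Step 3. Compare the arms.** The MTcap line carries no instruction to wait for session 1. A participant could hold 3 + 3 = 6 weeks of study supply beside the old bottle. The SGT+CBTI line does carry such an instruction, but it can be read as sealing the 30-day supply and the schedule together, or the schedule alone.

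**Step 4. Number of participants.** The remote share is not given. Assuming 10% to 90% of 132:

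- 0.10 × 132 = 13.2, about 13
- 0.90 × 132 = 118.8, about 119

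The count applies to those who receive study drug before session 1. Participants from the Loma Linda system have their study activities by telehealth.

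**Step 5. Upper bound on dose.** The exclusion criteria cap baseline dose at 8 mg/night diazepam-equivalent, and the planned reduction is about 25% per week. Whether week 1 is already reduced is not stated, so both cases are shown for a participant at the cap who takes both full supplies:

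- Week 1 reduced: 8 + 8 × (1 − 0.25) = 14 mg/night; 14/8 = 1.75 times the usual dose
- Week 1 at baseline dose: 8 + 8 = 16 mg/night; 16/8 = 2 times the usual dose

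The 8 mg figure is an eligibility limit, not an overdose threshold. Most participants would fall below these totals.

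**The case against.** The strongest reply is that the safeguard was never withdrawn. The safety plan applies it to both arms without limiting it to in-person sessions, and the telehealth amendment says intervention content is the same as in person. An interventionist on video can identify the old bottle and explain the replacement, and a remote participant probably has every medication within reach. In-person participants also take the old bottle home, in an envelope they could open. On this view, what is missing is a reminder aid and a shipping interval, which a session checklist could settle.

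There are other layers. Study supplies are labelled, and blister packs look unlike an ordinary bottle. Prescribers are told of the taper before randomization. MTcap participants record their perceived dose daily. CIWA-B, vital signs and the Epworth scale are collected weekly. The mailed education notebook, which is not part of the text reviewed, may carry a warning. The SGT+CBTI envelope may already keep the drug closed until session 1; even if it holds only the schedule, those participants have no schedule to start from.

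Much of this stands, and it limits the severity. It does not close the gap. The statement on identical content covers the intervention and the taper schedules; it supplies no envelope and does not delay delivery. Pharmacy labels and prescriber notice do not set the old bottle aside. Weekly measures could show over-sedation only after it has happened, and CIWA-B is a withdrawal scale. A notebook warning would help, but the protocol does not say there is one. None of these layers addresses the period between delivery and session 1 in MTcap.

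**Conclusion.** The concern holds. For remote participants, the plan as written omits the sealed, labelled envelope and allows both supplies to be in the home before the replacement instruction is given. The gap is clearest in MTcap and uncertain in SGT+CBTI because of the ambiguous mailing line. The sponsor should correct it; it is not a fatal flaw, because the verbal instruction and weekly monitoring remain.

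The size rests on assumptions. About 13 to 119 people follows from an assumed remote share with no basis in the documents, and it counts both arms. The 14 to 16 mg/night range is a worst case at the entry limit. Nothing in the documents indicates how often double dosing would occur. Confidence is medium, chiefly because the notebook and other participant materials could not be seen.

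**What to change.** - Add to the telehealth mailing list, and to pick-up packages, an envelope for the old hypnotic that already carries the safety plan's warning label.
- Mark study drug in both arms as not to be opened until session 1. This also settles what the SGT+CBTI envelope contains.
- Amend the duplicate-prescription item so that at a remote session 1 the participant identifies the old hypnotic and seals it on video, or confirms this verbally by telephone, and the interventionist records it.
- State what happens to mailed study drug if session 1 does not take place, for example return in the box already supplied.

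The cost is one envelope and label and a few minutes at session 1 per remote participant (about 13 to 119 envelopes under the assumed range), plus a short amendment. Dose, taper, later visits and analysis are unchanged. By telephone the step remains a verbal confirmation, so the gain there is mainly the labelled envelope and the hold on opening study drug.

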### Interventions

Both interventions will involve 8 sessions provided by a trained cognitive behavioral therapy for insomnia (CBTI) interventionist. The intervention period is expected to last approximately 9 weeks (but may be extended as described below). Both interventions include a tapering protocol for benzodiazepine use, behavioral therapy

for insomnia, plus weekly assessment for withdrawal symptoms. During week 7 and at the beginning of week 9 of the intervention, participants will only receive the withdrawal symptom assessment (see table to right). Participants will receive \$25 for attending the 2 withdrawal symptom assessments. The actual content and structure of the behavioral therapy and tapering protocol will differ between the two groups, although the dose reduction schedule will be the same for the two groups (described below). Intervention sessions will take place in designated, private research offices at VAGLA. All interventionist sessions will be audio-recorded and a random subset will be rated using a structured rating sheet to ensure fidelity to the treatment protocol. The interventionist will also maintain a session-by-session list of information covered and recommendations made. "Progress notes" will be maintained by the interventionist and reviewed during weekly "intervention meetings." These processes will ensure fidelity over the course of the study and avoid the risk of contamination across study arms.

| Week                      | Session | MTcap
Group SGT+CBTI Gr          |                    |  |  |
|---------------------------|---------|-------------------------------------|--------------------|--|--|
| 1                         | 1       | Intervention + BWA                  | Intervention + BWA |  |  |
| 2                         | 2       | Intervention + BWA Intervention +   |                    |  |  |
| 3                         | 3       | Intervention + BWA Intervention + B |                    |  |  |
| 4                         | 4       | Intervention + BWA                  | Intervention + BWA |  |  |
| 5                         | 5       | Intervention + BWA                  | Intervention + BWA |  |  |
| 6                         | 6       | Intervention + BWA Intervention + B |                    |  |  |
| 7                         |         | BWA only                            | BWA only           |  |  |

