# Extended taper plan

We have identified specific situations when the taper plan may need to be modified:

- a. Withdrawal symptoms/extended taper required: The taper may be extended up to a maximum of 16 weeks if the participant has withdrawal symptoms or cannot tolerate the scheduled taper, based upon changes in several of the CIWA-B items and vital signs, along with the patient's, interventionist's, and study physicians' judgments. In the MTcap group, an extended taper may be achieved by giving a duplicate 7-day blister pack (e.g., plateauing the doses until the participant is ready to move to the next blister pack). In the SGT+CBTI group, participants will be instructed to repeat a particular week in the printed taper schedule. Participants will continue to be monitored with weekly CIWA-B, vital signs, and the interventionist will review and reinforce key content of the intervention.
- b. Hypnotic dosed as "prn" at baseline: Taper schedules for participants who used their hypnotic "as needed" at baseline will be adjusted so that the starting week's total weekly hypnotic dose does not exceed the participants' total weekly baseline hypnotic dose.

For the MTcap group, the capsules on the predetermined drug-free days will be filled with an inert filler substance. The participants will still be instructed to take the capsule on a scheduled based nightly, not as needed. The use of capsules will ensure that the participant is not exposed to the drug more frequently than the baseline exposure. An increase in adherence to the taper protocol is one rationale for using capsules filled with inert filler substance rather than instructing participants not to take any capsule at all (i.e., similar to oral contraceptive inert pills that are provided in the monthly oral contraceptive pill pack). Another rationale for using insert capsules is related to our study's objective, which aims to develop an intervention for reducing placebo effects, such as the effects related to the conditioned response of taking the drug and attributing sleep and daytime function—which are known to vary from day to day—to the act of taking the pill.

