# Care coordination at end of intervention period

Participants in the MTcap group will be told the benzodiazepine dose that they are taking when they complete the intervention (or if they withdraw before the 9-week intervention period). The primary care providers of participants in both groups will be informed of the final medication regimen, so patients can continue to be monitored for withdrawal, if necessary.

At the last session of the intervention, the interventionist will use a debriefing script (see attached Debriefing Script) to inform MTcap participants of the actual doses that they were taking over the 9-week intervention. Participants will be given the taper schedule that the SGT+CBTI group followed (see attached Taper Schedule) unless there was a plateau in the tapering, in which case participants will be shown a revised taper schedule. The interventionist will tell participants the dose that they are currently taking and will review the last week's sleep diary to compare what participants thought they were taking with the actual dose. Participants will be given an opportunity to ask questions about the research, will be asked if they agree to allow the investigator to use the data collected up to that point in the study (additional data will be collected at post-treatment, and 6-months), and will be given contact information for the interventionist and [name].

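### The label on the retained old hypnotic bars use for 8 weeks only, although the taper may run to 16 weeks

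*Combined protocol and SAP*

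**What the plan says.** The item on duplicate prescriptions in the Potential Risks and Safety Plan recognises that a participant might take the study supply on top of the old one. Its safeguard is applied at the first session, to which participants in both arms bring their medicines. "The interventionist will identify the hypnotic that will be tapered and will place the bottle in a sealed envelope". The label outside reads "Do not take this medication during the 8-week SWITCH study unless instructed by the study staff", and the participant keeps the envelope.

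Other sections give longer periods. Under Interventions, "The intervention period is expected to last approximately 9 weeks". The care-coordination section describes debriefing MTcap participants on the "actual doses that they were taking over the 9-week intervention". The Extended taper plan says: "The taper may be extended up to a maximum of 16 weeks if the participant has withdrawal symptoms or cannot tolerate the scheduled taper". During an extension, "Participants will continue to be monitored with weekly CIWA-B, vital signs, and the interventionist will review and reinforce key content of the intervention".

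For remote participants, the telehealth amendment under Interventions begins its list with "Prior to the first intervention session, the following materials will be mailed to participants". The list includes study drug for both arms, a sealed envelope holding the SGT+CBTI taper schedule, and a box for sending back unused drug. It includes no envelope or label for the old bottle. The same amendment says that intervention content and taper schedules match the in-person sessions.

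**The concern.** The label is the only written instruction attached to a bottle of active hypnotic that stays in the participant's hands, and it states a period that the protocol itself can exceed. A participant still tapering in week 10 or 14 could read it as having lapsed. Extensions are granted for withdrawal symptoms or difficulty with the schedule, so the participants who outlast the label are those with most reason to open the envelope. The plan names the harm it wants to avoid: a dose above the one prescribed, with possible sleepiness or dizziness, here in older adults.

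The remote route raises a related question. The safeguard as written needs the interventionist to handle the bottle, and the protocol does not say how this is done when the session is by video or telephone. Remote delivery is not marginal: it may follow participant preference, and participants from Loma Linda take part by telehealth.

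**Working it through.** There is no statistical figure to reproduce. The check compares durations and then compares two procedures.

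**Inputs**
- Period on the label: 8 weeks (Potential Risks and Safety Plan).
- Planned intervention: about 9 weeks (Interventions; Care coordination at end of intervention period).
- Usual blister-pack supply: 8 weeks, given as an example (preparation of hypnotics, MTcap group).
- Longest permitted taper: 16 weeks (Extended taper plan).
- Final MTcap pack: 4 placebo capsules and 3 empty blisters, so no active drug (MTcap hypnotic taper protocol).
- Contingency plateau supply in the first MTcap telehealth mailing: 3 weeks.

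**Assumption.** The label period and the taper both start at session 1, when the label is affixed and study drug begins.

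**Label shortfall = treatment period - 8 weeks**
1. Planned course, counting the 8-week supply: 8 - 8 = 0 weeks. Counting the 9-week intervention: 9 - 8 = 1 week. The last pack carries no active drug, so there is little or nothing to double at that point.
2. Illustration with three plateau weeks: 8 + 3 = 11 or 9 + 3 = 12 weeks, so 11 - 8 = 3 to 12 - 8 = 4 weeks.
3. Longest taper: 16 - 8 = 8 weeks, or 8 x 7 = 56 nights. The label then covers 8/16, or half, of the taper.

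The closing words of the label, which allow for staff instruction, do not lengthen it. They make an exception to a ban that is itself limited to the stated period.

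**Seal-and-label step, in person and remote**
- In person: the participant brings the bottle, and the interventionist identifies it, seals it and labels it.
- Remote: study drug arrives before session 1. The only sealed envelope on the mailing list is for the SGT+CBTI schedule, and the return box is for unused medication. The telephone option refers back to the video procedure, the remote drug-distribution text covers mailing and pick-up, and the telehealth safety text covers emergencies and identity and privacy checks. None of these describes a remote version of the step.

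**The case against.** The strongest reply is that the plan is guarding against confusion, which is greatest at session 1. By week 9 a participant on an extended taper has used study packs for two months, has been through a plateau decision with a study physician, and is still seen weekly. Nothing in the documents shows that anyone would treat the label as expired. Opening the envelope during withdrawal would be a deliberate act, which label wording may do little to prevent. This stands as an argument that the harm is unlikely. It does not alter the fact that the written instruction is shorter than the treatment it covers.

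On the remote step, session content is stated to be identical, the education notebook is not among the documents, and a participant can put a bottle in any envelope while the interventionist watches. A reader might infer that remote participants get no safeguard at all. The documents do not support that: they show only that no remote version is described and that the listed mailing lacks the materials.

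A reader might also infer that refills during the taper would go unnoticed and that a weekly question about them is required. The listed weekly measures do not include one, but prescribers are told of the plan before randomization and can block it, the study prescription is entered in CPRS, progress notes are reviewed weekly, CURES is queried at baseline and post-treatment, and the sleepiness check allows for "a newly-prescribed medication from the individual's physician". A routine refill question would be a preference about undescribed detail, not a correction of a defect.

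**Conclusion.** The label should be corrected. On a literal reading, and with both periods counted from session 1, it stops short of the taper by up to 8 weeks at the 16-week maximum and by 0 to 1 week on the planned course, where the gap is minor. This part does not depend on unseen attachments, because the label text is given in full. The missing remote materials are a fair secondary point, limited to what is described.

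Two stronger statements are not available. The number of participants affected cannot be given: the plan calls withdrawal that changes the protocol uncommon and states no rate. Nor can the size of a double dose be given, because the dose in any week depends on a taper schedule that is an attachment outside the documents. The point is a low-cost tightening of a safety procedure, to be considered by the sponsor. It has no effect on sample size, power or analysis.

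**What to change.** Strike the phrase that ties the label to an eight-week study, leaving the prohibition and its existing exception for staff instruction. The result has no end date and still lets study physicians direct a change. A label that ran until the end of the taper would close the same gap but should be avoided: it would imply that the old hypnotic may be resumed afterwards, which works against the discontinuation outcome in Aim 1.

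Add an envelope and a printed label to the telehealth mailing. State that at session 1 the participant seals the old bottle with the interventionist guiding by video or, if video fails, by telephone.

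The cost is a reworded label, one small addition to an existing mailing and a few minutes in a session that already takes place. No material downside is apparent.
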